14 STATISTICAL CONSIDERATIONS

The study consists of a single stage of accrual of patients with hepatic metastases from colorectal cancer.

Patient safety will be assured by monitoring the number of patients who fail to receive the first six scheduled vaccinations because of toxicity. If three or more patients experience grade 4 or worse toxicity due to the vaccine before completing six immunizations, the study will be terminated. If the unknown true rate of grade 4 or worse toxicity is 0.05, then the probability of early termination is 0.04. Similarly, if the unknown true rate is 0.25, then the probability of early termination is 0.76.

Feasibility will be assessed by the ability to make vaccine from resected hepatic metastases in quantities sufficient for six vaccinations. Fifteen patients will be entered. If fewer than 9 patients receive six vaccinations, the study will cease. A success rate under 65% (true rate) may imply that the method needs further development or that the amount of tissue available in this population limits the feasibility of this strategy. This study will have 75% power against the null of 45% success rate, testing at the one-sided 0.18 significance level and using exact methods.

The percentage of patients who successfully receive 6 vaccinations and the number of vaccinations received by patients will be described. Any late occurrences of grade 3 or worse toxicity and the vaccination number at which they occur will be reported.

For the correlative science it is unclear which changes will occur in the circulating immune cells since a study like this has never been done in patients with resected hepatic metastases from colorectal cancer. Currently we do not have estimates to present a statistical model or plan. No changes in the correlative science should influence administration of the vaccine in the patients.

Table 1. 90% confidence intervals for the true proportion of patients who receive all six injections

Observed number of	Observed rate of patients	90% confidence interval for
--------------------	---------------------------	-----------------------------

patients who receive all six injections	who receive all six injections	the true rate of patients who receive all six injections
8	53%	(30%, 76%)
10	67%	(42%, 86%)
11	73%	(49%, 90%)
12	80%	(56%, 94%)

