14.3 Reporting and Exclusions

- 14.3.1 **Feasibility**- Feasibility will be defined by the capacity for patients in this specific population to initiate the vaccination process, i.e., to receive at least one vaccination. This will be governed by the ability to successfully harvest a minimum number of viable tumor cells at the time of surgery.

At the treating physician's discretion, patients with progressive disease or treatment-related complications between surgery and initiation of vaccination who are deemed incapable of or inappropriate for treatment will not initiate vaccination and will be included in the feasibility analysis.

We will consider this treatment plan feasible in this patient population if at

least 60% of initially enrolled patients go on to begin vaccination.

If an enrolled patient withdraws from the study for a reason that is not associated with surgical morbidity or disease progression, that patient will not be counted in the feasibility analysis.

14.3.2 **Safety and Biologic Activity:** All participants who receive at least one vaccine will be considered evaluable for toxicity. All participants who receive all 6 vaccines will be evaluable for biologic response.

14.3.3 **Evaluation of response.** All participants included in the study must be assessed for response to treatment, even if there are major protocol treatment deviations or if they are ineligible. Each participant should be assigned one of the following categories: 1) complete response, 2) partial response, 3) stable disease, 4) progressive disease, 5) early death from malignant disease, 6) early death from toxicity, 7) early death because of other cause, or 9) unknown (not assessable, insufficient data). By arbitrary convention, category 9 usually designates the "unknown" status of any type of data in a clinical database.

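### Two feasibility rules use the same 9-of-15 cut-off on different events (six doses received versus one), and nothing says which governs

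*Combined protocol and SAP*

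**What the plan says.** The feasibility paragraph of Section 14 opens: "Feasibility will be assessed by the ability to make vaccine from resected hepatic metastases in quantities sufficient for six vaccinations". It enters fifteen patients and then gives the decision rule: "If fewer than 9 patients receive six vaccinations, the study will cease". The operating characteristics follow in the same paragraph: "This study will have 75% power against the null of 45% success rate, testing at the one-sided 0.18 significance level", by exact methods. A true rate of 65% is mentioned as the level below which the method may need more work. Table 1 in the same section gives "90% confidence intervals for the true proportion of patients who receive all six injections".

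Section 14.3.1 defines feasibility as the capacity to start the process, that is, "to receive at least one vaccination". The plan is judged feasible if at least "60% of initially enrolled patients go on to begin vaccination". Patients with progression or complications between surgery and vaccination who are judged unfit "will not initiate vaccination and will be included in the feasibility analysis". For a patient who withdraws for a reason unconnected with surgical morbidity or progression, the rule is: "that patient will not be counted in the feasibility analysis".

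Section 14.1.1 lists the feasibility of manufacture as a primary endpoint and gives no criterion. Section 1.2 lists only safety as primary.

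**The concern.** Sixty per cent of 15 is 9, so the two rules look alike. They count different events: six doses received in Section 14, one dose received in 14.3.1. Neither section refers to the other and no other section sets an order of precedence, so the feasibility verdict can depend on which paragraph the analyst follows.

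A third event is also in play. The opening sentence of Section 14 and 14.1.1 are about manufacture. Neither count isolates it. The begin count loses patients to progression or complications before the first dose. The six-dose count also loses those who stop after starting, for the reasons listed in 5.5.

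The denominators appear to differ too. Section 14 uses a fixed 9 among 15 entered. Section 14.3.1 removes some withdrawals from a percentage it bases on those initially enrolled, and it is unclear whether that exclusion reaches Section 14.

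Feasibility is primary under 14.1.1 and is the only endpoint with a stated significance level and power. If 14.3.1 is followed, the 0.18 level gives no protection against declaring feasibility when the six-dose rate sits at the 45% null.

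**Working it through.** **Inputs.** From Section 14: n = 15, cut-off 9, null 45%, 65% read as the alternative (the text does not label it so), level 0.18, power 75%. From 14.3.1: threshold 60%. Success is read as receipt of six doses, as in Table 1. The documents give neither a start rate nor a completion rate, so those below are assumptions. Patients are taken as independent, and all 15 are counted unless stated.

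**Step 1: the plan's own figures.** With X ~ Binomial(15, p), the level is P(X ≥ 9) at p = 0.45 and the power is P(X ≥ 9) at p = 0.65.

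| Cut-off | Level (p = 0.45) | Power (p = 0.65) |
|---|---|---|
| 8 | 0.346 | 0.887 |
| 9 | 0.182 | 0.755 |
| 10 | 0.077 | 0.564 |

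Only 9 matches the stated 0.18 and 75%. Exact (Clopper-Pearson) 90% intervals for 8, 10, 11 and 12 of 15 are (30%, 76%), (42%, 86%), (49%, 90%) and (56%, 94%), which are the four rows of Table 1. The arithmetic of Section 14 is sound.

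**Step 2: direction of conflict.** Everyone who receives six has begun, so with all 15 counted the only possible conflict is 9 or more beginning (feasible by 14.3.1) with fewer than 9 receiving six (cease by Section 14). Let s be the start rate and p6 the six-dose rate. Then

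P(conflict) = P(Bin(15, s) ≥ 9) − P(Bin(15, p6) ≥ 9).

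Example: s = 0.80 and p6 = 0.65 give 0.982 − 0.755 = 0.227.

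**Step 3: size of the conflict.** The share of starters who finish is p6/s.

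| p6 | s | Implied finishing share | P(9 or more begin) | P(conflict) |
|---|---|---|---|---|
| 65% | 65% | 100% | 0.755 | 0 |
| 65% | 70% | 93% | 0.869 | 0.114 |
| 65% | 80% | 81% | 0.982 | 0.227 |
| 65% | 100% | 65% | 1.000 | 0.245 |
| 45% | 45% | 100% | 0.182 | 0 |
| 45% | 60% | 75% | 0.610 | 0.428 |
| 45% | 70% | 64% | 0.869 | 0.687 |
| 45% | 80% | 56% | 0.982 | 0.800 |
| 45% | 100% | 45% | 1.000 | 0.818 |

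If instead 90% of starters finish, so that p6 = 0.9s, P(conflict) is 0.19, 0.17, 0.08 and 0.01 for start rates of 60%, 70%, 80% and 90%.

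**Step 4: denominator.** Suppose 8 of 15 begin and 2 others withdraw for uncounted reasons. Under 14.3.1, 8/(15 − 2) = 8/13 = 62%, which is feasible. On all entered, 8/15 = 53%, and 9 receiving six is impossible.

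**The case against.** The best defence is that the two rules do different jobs: 14.3.1 defines feasibility as starting, and Section 14 adds a cease rule. That reading is possible. However, the cease sentence, null rate, level and power all sit in the paragraph that says how feasibility will be assessed, and Table 1 tabulates receipt of six. On that reading, the plan's only stated test would concern something other than its feasibility definition.

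Second, Section 7.3 prepares at least six aliquots for each patient, and 14.3.1 ties starting to the cell harvest. A first-round starter should therefore already have six doses made, so beginning is a fair proxy for manufacture. This stands in part. It narrows the gap to losses before the first dose and between the first and sixth, but it does not reconcile the two rules.

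Third, the large null-case figures need only 45% to 75% of starters to finish. A 57-day course with local toxicities in the earlier trial suggests less loss, though no completion rate is given. This stands as a limit on size, and the 90%-finishing figures reflect it. Likewise, 0.61, 0.87 and 0.98 are not error rates of a start criterion taken on its own terms. They matter only if passing it is read as success on the six-dose question.

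Fourth, the exclusion in 14.3.1 may be meant to apply to Section 14 as well. That is possible, but the text does not say so.

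Last, accrual is single-stage with no stated interim look, Section 14 already commits to describing how many doses patients receive, and the safety rule also has stated termination probabilities (0.04 and 0.76). These points limit the harm during the trial. They do not settle the end-of-study verdict.

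**Conclusion.** The concern holds and must be fixed. One set of counts, such as 12 beginning and 8 receiving six, is both feasible and a reason to cease. This is a contradiction in a decision rule, not missing detail. The stated 0.18 and 75% are correct for 9 of 15 receiving six, and no operating characteristics are given for the begin rule. At a true six-dose rate of 45%, the begin rule would declare feasibility with probability 0.61, 0.87 or 0.98 at start rates of 60%, 70% or 80%.

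The contradiction is certain from the text. Its probability is not: it is negligible if nearly everyone starts and finishes, and substantial if many stop after the first dose. In a 15-patient trial the choice of rule could also be made after the counts are seen.

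**What to change.** Reconcile Sections 14, 14.1.1 and 14.3.1 to one feasibility event, one denominator and one governing rule, chosen by the sponsor before the feasibility counts are known, with level and power stated for that event.

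- **Receipt of six.** Keeping at least 9 of all 15 entered preserves the cut-off, level, power and Table 1. The 60%-begin figure becomes descriptive. Section 14.1.1 is reworded to match, or marked as estimated without a decision rule.
- **Manufactured for six.** The cease sentence and Table 1 need rewording.
- **Beginning.** The 45% and 65% rates need restating for that event.

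Under any choice, report manufactured-for-six, began and completed-six as separate proportions with exact 90% intervals, and base conclusions about the method or the amount of tissue on the first. Optionally add the row for the cut-off itself to Table 1: 9 of 15, (36%, 81%).

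The cost is an amendment approved by the IRB (13.1). Counting all 15 makes unrelated withdrawals non-successes, which departs from 14.3.1, lowers the observed rate and can change the verdict (8/13 = 62% becomes 8/15 = 53%). Section 12.1.2 lists no form dedicated to manufacture, so unless an existing form captures it, that count has to come from the cell facility's production records.

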14.1 Study Design/Endpoints

Primary

- 14.1.1 To determine the feasibility of manufacturing lethally irradiated, autologous colorectal cancer cells engineered by adenoviral mediated gene transfer to secrete GM-CSF from hepatic metastases.
- 14.1.2 To determine the safety and biologic activity of vaccination with lethally irradiated, autologous colorectal cancer cells engineered by adenoviral mediated gene transfer to secrete GM-CSF in stage IV colorectal cancer patients.

Secondary

- 14.1.3 To determine the progression free survival and two-year survival of stage IV colorectal cancer patients vaccinated with lethally irradiated, autologous colorectal cancer cells engineered by adenoviral mediated gene transfer to secrete GM-CSF

14.2 Sample Size/Accrual Rate

The plan is to enroll 15 patients within two (2) years.

14.3 Reporting and Exclusions

- 14.3.1 **Feasibility**- Feasibility will be defined by the capacity for patients in this specific population to initiate the vaccination process, i.e., to receive at least one vaccination. This will be governed by the ability to successfully harvest a minimum number of viable tumor cells at the time of surgery.

At the treating physician's discretion, patients with progressive disease or treatment-related complications between surgery and initiation of vaccination who are deemed incapable of or inappropriate for treatment will not initiate vaccination and will be included in the feasibility analysis.

We will consider this treatment plan feasible in this patient population if at

least 60% of initially enrolled patients go on to begin vaccination.

If an enrolled patient withdraws from the study for a reason that is not associated with surgical morbidity or disease progression, that patient will not be counted in the feasibility analysis.

14.3.2 **Safety and Biologic Activity:** All participants who receive at least one vaccine will be considered evaluable for toxicity. All participants who receive all 6 vaccines will be evaluable for biologic response.

14.3.3 **Evaluation of response.** All participants included in the study must be assessed for response to treatment, even if there are major protocol treatment deviations or if they are ineligible. Each participant should be assigned one of the following categories: 1) complete response, 2) partial response, 3) stable disease, 4) progressive disease, 5) early death from malignant disease, 6) early death from toxicity, 7) early death because of other cause, or 9) unknown (not assessable, insufficient data). By arbitrary convention, category 9 usually designates the "unknown" status of any type of data in a clinical database.

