5.2 Pre-treatment Criteria

5.2.1 Primary Tumor Procurement

5.2.1.1 Patients will undergo a surgical procedure (hepatic resection) to obtain tissue for vaccine preparation.

5.2.1.2 The responsible surgeon will send a portion of the tumor for standard of care pathology review. Then, the surgeon will place the research tumor specimen in sterile media in a sterile container. After gross evaluation by the pathologist of

the entire specimen in the operating room, the tissue will be transferred to the authorized study team member for vaccine processing at the DFCI CMCF.

5.2.1.3 Patients will receive routine post-operative care.

5.2.1.4 At the discretion of the treating physician patients may receive post operative chemotherapy prior to vaccine administration. Participants will undergo a separate standard of care chemotherapy consent session with their treating physician as the chemotherapy is not a part of the investigational agent in this study.

5.2.1.5 If recurrent disease is identified on the restaging scans prior to vaccine, vaccine will not be administered.

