6.3 Dose Modifications/Delays

6.3.1 There will be no dose adjustments for Grade 1 and 2 toxicities seen on this study.

6.3.2 If a patient develops grade 3 toxicity attributable to the vaccine, additional treatment will be withheld until all toxicity has resolved, then he or she may be retreated at monthly intervals. If the toxicity recurs with resumption of vaccine then the patient will be removed from study. If a patient develops a grade 4 toxicity attributable to the vaccine, he or she will be removed from study. If three grade 4 or greater toxicities attributable to the vaccine are observed at any time, the trial will be suspended to investigate the causes of these unexpected toxicities.

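### The primary feasibility endpoint is manufacture, but both decision rules count vaccine received, and the 14.3.1 withdrawal exclusion does not say that a failed lot stays in as a failure

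*Combined protocol and SAP*

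**What the plan says.** Section 14.1.1 gives the first primary endpoint as "To determine the feasibility of manufacturing lethally irradiated, autologous colorectal cancer cells". Section 14 opens its feasibility paragraph in the same sense: "Feasibility will be assessed by the ability to make vaccine from resected hepatic metastases in quantities sufficient for six vaccinations".

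The rules then count something else.

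- **Section 14:** "Fifteen patients will be entered", and "If fewer than 9 patients receive six vaccinations, the study will cease". This rule carries a null rate of 45%, a one-sided level of 0.18 and 75% power. A true success rate below 65% "may imply that the method needs further development or that the amount of tissue available in this population limits the feasibility of this strategy".
- **Section 14.3.1:** feasibility is receipt of at least one vaccination, and the plan is feasible if 60% or more of those initially enrolled begin. Patients who progress or have treatment-related complications before vaccination, and so never start, stay in the analysis. An enrolled patient who "withdraws from the study for a reason that is not associated with surgical morbidity or disease progression" is left out of it.

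Other sections create losses after a lot exists.

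- Section 5.2.1.5: "If recurrent disease is identified on the restaging scans prior to vaccine, vaccine will not be administered".
- Section 5.5 ends treatment on progression.
- Section 6.3.2 removes patients for grade 4 toxicity attributed to the vaccine and, for grade 3, says: "If the toxicity recurs with resumption of vaccine then the patient will be removed from study".
- Section 5.1.2 sets a 6-month limit from operation to first dose while allowing chemotherapy in between.

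**The concern.** Making a lot and delivering it are different events, separated by months in which disease course, surgical recovery, chemotherapy and toxicity all act. A count of doses received mixes them. If the count is low, the plan's own interpretation points to the method or the amount of tissue, although the lots may all have been good. A sound manufacturing process could then be judged to need more development.

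The withdrawal exclusion raises a second, narrower problem, confined to 14.3.1. A failed lot is neither surgical morbidity nor progression. A patient who is told that no vaccine exists and then withdraws fits the literal wording of the exclusion and leaves the denominator. With 15 patients, how a few such cases are recorded can change the conclusion.

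**Working it through.** **Inputs from the documents.** n = 15; cut-off 9 receiving six doses; null 45%; alternative 65%; level 0.18; power 75% (Section 14). Threshold 60% (14.3.1); 60% of 15 is 9, so with nobody excluded both rules use the same cut-off.

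**Assumed, because the documents give no figure.** q, the share of patients with a lot made who are later lost for other reasons, 0 to 30%, independent of manufacture. w, the share of lot failures recorded as withdrawals, 0 to 100%. A true manufacture rate m of 80% is used as an illustration beside the plan's 45% and 65%.

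**1. The plan's own figures.** With X ~ Binomial(15, p):

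- P(X ≥ 9 | p = 0.45) = 0.182, stated as 0.18.
- P(X ≥ 9 | p = 0.65) = 0.755, stated as 75%.

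Both reproduce. They describe manufacture only if every patient with a lot made is also counted as a success, that is, q = 0.

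**2. Later losses.** The counted success probability is p = m(1 − q).

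| q | m = 0.65: p | P(X ≥ 9) | m = 0.80: p | P(X ≤ 8) |
|---|---|---|---|---|
| 0 | 0.650 | 0.755 | 0.80 | 0.018 |
| 10% | 0.585 | 0.563 | 0.72 | 0.097 |
| 20% | 0.520 | 0.361 | 0.64 | 0.272 |
| 30% | 0.455 | 0.192 | 0.56 | 0.516 |

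At m = 65% and q = 30%, the chance of passing (0.192) is close to the chance at the null rate of 45% (0.182).

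Which losses make up q depends on the rule. Recurrence or complications before vaccination count under both. Toxicity and progression during vaccination count only under the six-dose rule, because those patients have already begun.

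**3. A worked count.** All 15 lots are made and 7 patients recur before vaccine. Manufacture is 15/15 = 100%. Eight begin, so 14.3.1 gives 8/15 = 53%, below 60%. At most 8 can receive six doses, which is fewer than 9. Both rules fail.

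**4. The withdrawal exclusion, 14.3.1 only.** With s starters and d patients excluded, the rule is s/(15 − d) ≥ 0.60. Take no losses other than failed lots.

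- 7 starters, 8 lot failures: 7/15 = 47% if all count, 7/7 = 100% if all are excluded. The verdict turns at d = 4, since 7/12 = 58% and 7/11 = 64%.
- 8 starters, 7 lot failures: 8/15 = 53% if all count. The verdict turns at d = 2, since 8/14 = 57% and 8/13 = 62%.
- 9 starters, 6 lot failures: 9/15 = 60% already passes, so excluding the failures changes the percentage but not the verdict.

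As a probability, at m = 45% and q = 0, sum the multinomial over starter (m), excluded ((1 − m)w) and counted failure ((1 − m)(1 − w)) wherever the 60% rule is met. The chance of declaring feasibility is 0.18, 0.31, 0.59 and 1.00 for w = 0, 25%, 50% and 100%.

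**The case against.** The strongest reply is that deliverability is a legitimate Phase I question and that the plan chose it. Section 1.1 speaks of the feasibility of a vaccination strategy; 14.3.1 asks whether the treatment plan is feasible in this population and deliberately keeps progressors in. The interpretation in Section 14 is hedged, and that section separately watches losses due to toxicity and describes the number of vaccinations received. All of this stands as a defence of reporting delivery. It does not defend using delivery as the sole test of an endpoint that the plan calls manufacture.

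Three stronger readings are tempting, and the documents do not support them.

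- **A reader might infer that the plan excludes manufacturing failures.** No section says that a failed lot is recorded as a withdrawal. Section 4.1 requires only a change of protocol status for a registered patient who is not treated. Section 14.3.1 ties feasibility to harvesting enough viable cells and refers to patients initially enrolled, which suggests that such patients count. The literal wording permits the exclusion but does not require it.
- **A reader might infer that the results say nothing about manufacture.** Both counts depend on manufacture, since nobody is vaccinated without a lot. They do not isolate it. Cell yield also sets each patient's dose (Sections 5.2.2.5 and 7.3), so lot success could be reported; the plan does not say that it will be.
- **A reader might infer that the count is distorted in both directions under either rule.** The withdrawal exclusion appears only in 14.3.1. Section 14 works from 15 entered patients and states no exclusion.

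**Conclusion.** The point holds in this form. Manufacture is the stated endpoint, receipt is what is counted, and losses unrelated to manufacture are scored as failures. The stated level and power reproduce but apply to manufacture only without such losses; at 65% true manufacture, losses of 10% to 30% lower the 0.755 to between 0.563 and 0.192. That range rests on assumed loss rates and on independence of loss from manufacture. The 8/15 example needs neither assumption.

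The missing exception in the withdrawal exclusion is an ambiguity within 14.3.1. It matters only if lot failures are recorded as withdrawals. With failed lots as the only losses, it changes the verdict only when at least seven of the 15 lots fail.

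This should be fixed. In an uncontrolled 15-patient Phase I trial it does not invalidate the design, but it limits what a negative feasibility result can be taken to mean.

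**What to change.** 1. Define the manufacturing endpoint as the proportion of all enrolled, resected patients whose lot yields at least six aliquots at or above the minimum stated in Section 7.3. No resected patient leaves this denominator, whatever happens later. Base the method-or-tissue interpretation on this proportion.
2. Report delivery separately, as the numbers who began vaccination and who received all six, with the reason for each shortfall: lot failure, recurrence, surgical morbidity, toxicity, start window missed, or patient choice.
3. State in 14.3.1 that lot failure is never an excluded withdrawal. Voluntary withdrawal after a successful lot may be excluded from the delivery measure only; excluding it from the manufacturing figure would discard known successes.
4. State which measure the 9-of-15 rule and the 45% and 65% rates govern, and reconcile Section 14 with 14.3.1. Those rates are now attached to receiving six vaccinations. Moving them to manufacture would lower the bar, so the sponsor should decide this explicitly.

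The cost is a wording change in Sections 14 and 14.3.1 and two feasibility figures in place of one. Yield is already determined for each lot in order to set the dose, so no new assay is needed.
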